9.5. Record Keeping

9.5.1. Health Insurance Portability Accountability Act of 1996

The investigator agrees to comply with all applicable federal, state, and local laws and regulations relating to the privacy of subject health information, including, but not limited to, the Standards for Individually Identifiable Health Information, 45 CFR. Parts 160 and 164 (the Health Insurance Portability Accountability Act of 1996 [HIPAA] Privacy Regulation). The investigator shall ensure that study subjects authorize the use and disclosure of protected health information in accordance with HIPAA Privacy Regulation and in a form satisfactory to the sponsor. See **Appendix F** for Investigator Obligations.

9.5.2. Financial Disclosure

The investigator shall provide to the sponsor sufficient accurate financial information to allow the sponsor and Westat to submit complete and accurate financial certification or disclosure statements to the FDA. The investigator shall promptly update this information if any relevant changes occur in the course of the study or for one year following completion of the study.

9.5.3. Access to Original Records

It is an expectation of regulatory authorities that monitors, auditors, and representatives of national and international government regulatory agency bodies have access to original source documentation to ensure data integrity. “Original” in this context is defined as the first documentation of an observation and does not differentiate between hard copy and electronic records.

9.5.4. Retention of Study Documents

Study-related records must be retained for at least 2 years after the last approval of a marketing application in an ICH region and until there are no pending or contemplated marketing applications in an ICH region, or at least 2 years have elapsed since the formal discontinuation of clinical development of the investigational product. These documents should be retained for a longer period, however, if required by applicable regulatory requirements or by an agreement with the sponsor.

The investigator must not destroy any study-related records without receiving approval from the sponsor. The investigator must notify the sponsor in the event of accidental loss

or destruction of any study records. If the investigator leaves the institution where the study was conducted, the sponsor must be contacted to arrange alternative record storage options.

10. ADMINISTRATIVE STRUCTURE OF THE STUDY

Westat will be responsible for data management, statistical analyses, and clinical study report writing. Clinical monitors under the direction of Westat will be used to monitor the study. Clinical laboratory parameters will be assessed by local laboratories and results recorded in the CRF module.

Appendix A. Number of Tablets to be Administered Per Dose Level**Dose Level 50 mg/m² BID**

Body Surface Area (m ²)	Total mg each Dose	Number Tablets Each Dose (50 mg)	Number Tablets Each Dose (200 mg)
≤ 2.00	100	2	0
2.01 – 3.49	150	3	0
≥ 3.5	200	0	1

Dose Level 100 mg/m² BID

Body Surface Area (m ²)	Total mg each Dose	Number Tablets Each Dose (50 mg)	Number Tablets Each Dose (200 mg)
≤ 1.50	150	3	0
1.51 – 2.00	200	0	1
≥ 2.01	250	1	1

Dose Level 200 mg/m² BID

Body Surface Area (m ²)	Total mg each Dose	Number Tablets Each Dose (50 mg)	Number Tablets Each Dose (200 mg)
≤ 1.25	250	1	1
1.26 – 1.62	300	2	1
1.63 – 1.87	350	3	1
1.88 – 2.12	400	0	2
≥ 2.13	450	1	2

Dose Level 300 mg/m² BID

Body Surface Area (m ²)	Total mg each Dose	Number Tablets Each Dose (50 mg)	Number Tablets Each Dose (200 mg)
≤ 1.37	400	0	2
1.38 – 1.51	450	1	2
1.52 – 1.65	500	2	2
1.66 – 1.77	550	3	2
1.78 – 2.05	600	0	3
2.06 – 2.17	650	1	3
≥ 2.18	700	2	3

Dose Level 400 mg/m² BID

Body Surface Area (m²)	Total mg each Dose	Number Tablets Each Dose (50 mg)	Number Tablets Each Dose (200 mg)
≤ 1.25	500	2	2
1.26 – 1.37	550	3	2
1.38 – 1.51	600	0	3
1.52 – 1.65	650	1	3
1.66 – 1.77	700	2	3
1.78 – 1.91	750	3	3
1.92 – 2.05	800	0	4
2.06 – 2.17	850	1	4
≥ 2.18	900	2	4

Appendix B. FF-10501-01 Dosing Delays and Dose Modifications

Toxicity CTCAE Grade	During a Course of Therapy	Dose Adjustment for Next Treatment, (mg/m ²) BID* (%)				
		50	100	200	300	400
Grade 1	Maintain dose level					
Grade 2						
-1 st occurrence	Interrupt until resolved to Grade 0-1	50 (100%)	100 (100%)	200 (100%)	300 (100%)	400 (100%)
-2 nd occurrence	Interrupt until resolved to Grade 0-1	-	50 (50%)	150 (75%)	225 (75%)	300 (75%)
-3 rd occurrence	Interrupt until resolved to Grade 0-1	-	-	100 (50%)	150 (50%)	200 (50%)
-4 th occurrence	Discontinue treatment permanently OR dose reduce (200 – 400 mg/m ² BID dose groups only)	-	-	50 (25%)	75 (25%)	100 (25%)
Grade 3						
-1 st occurrence	Interrupt until resolved to Grade 0-1	-	50 (50%)	150 (75%) 100 (50%) 50 (25%)	225 (75%) 150 (50%) 75 (25%)	300 (75%) 200 (50%) 100 (25%)
-2 nd occurrence	Interrupt until resolved to Grade 0-1	-	-			
-3 rd occurrence	Discontinue treatment permanently OR dose reduce (200 – 400 mg/m ² BID dose groups only)	-	-			
Grade 4						
-1 st occurrence	Discontinue permanently, OR, if physician deems it to be in the subject's best interest to continue, interrupt and/or dose reduce until resolved to Grade 0-1 (200 – 400 mg/m ² dose groups only)	-	-	100 (50%) 50 (25%)	150 (50%) 75 (25%)	200 (50%) 100 (25%)

*Round up calculated unit dose to next unit dose based on tablet dose strength

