1.3.3. Phase 2 Study in Advanced Hematologic Malignancies

A larger Phase 2 study was conducted in patients with advanced hematologic malignancies.⁷ A total of 165 patients were enrolled; 85 had received prior therapy with antimetabolites, including 6-MP or cytosine arabinoside (ara-C). Patients were treated with SM-108 orally, at doses of 70, 200 or 300 mg/m² BID (140, 400 or 600 mg/m²/day). In 39 patients with chronic myelogenous leukemia (CML), 21 had complete responses (CRs) and 6 had PRs for an OR rate of 69%. Among 30 patients with AML, 7 had PRs (23%). Among 36 patients with MDS, 1 had a CR, 12 had PRs for an ORR of 36%. For 13 patients with polycythemia rubra, 4 had CRs and 7 had PRs for an ORR of 84.6%). The RR rate was highest in patients with CML and MDS at doses of \geq 600 mg/m²/day. Clinical responses by dose are described in **Table 1**.

Table 1. Phase 2 Study in Hematologic Malignancies: Clinical Response by Dose

Diagnosis Dose (mg/day)	CML	MDS				Polycythaemia vera	AML	Total (%)
		CMMoL	RAEB	RAEB in T	Total			
< 200			1/2		½		0/2	1/4 (25)
200 to < 400	1/1	1/1	0/1	0/3	1/5	2/2	1/3	5/11 (45.5)
400 to < 600	2/4	0/1	2/7	0/3	2/11	3/3	2/11	9/29 (31)
600 to < 800	20/22	4/7	2/3	2/4	8/14	6/8	2/10	36/54 (66.7)
800 to < 1000	4/11	0/2	0/1	1/1	¼		2/4	7/19 (36.8)
1000 \leq	0/1							0/1
Total (%)	27/39 (69.2)	5/11 (45.5)	5/14 (35.7)	3/11 (27.3)	13/36 (36.1)	11/13 (84.6)	7/30 (23.3)	58/118 (49.1)

The most commonly reported adverse events were gastrointestinal (nausea, anorexia, vomiting, abdominal discomfort; 66%), followed by allergic symptoms (rash, pruritis; 1%). Changes in laboratory values occurred in 30 of 165 (18%) of patients, all were transient/reversible and most were \leq Grade 2. A total of 14 patients (8%) experienced bone marrow suppression (neutropenia, thrombocytopenia, reduced Hb). The nadir was reached in 2 -3 weeks for white blood cell (WBC) count and platelets, 5 weeks for Hb, and recovery from nadir to pre-dose values was approximately 2 weeks (**Table 2**).

Table 2. Phase 2 Study Hematologic Malignancies: Adverse Events in $\geq 2\%$ Patients

Total Number of Patients		165
Number of Patients Reporting (%)	Increased ALT	16 (9.7)
	Nausea	15 (9.1)
	Increased AST	14 (8.5)
	Loss of appetite	11 (6.7)
	Decreased platelet count	8 (4.8)
	Rash	7 (4.2)
	Vomiting	6 (3.6)
	Decreased hemoglobin	4 (2.4)
	Abdominal discomfort	3 (1.8)
	General malaise	3 (1.8)
	Decreased WBC	3 (1.8)
	Increased total bilirubin	3 (1.8)
	Increased GTP	3 (1.8)

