5.4.2. Instructions Regarding Dose Delays and Dose Modifications

Adverse events considered for treatment interruption and dose reduction will exclude the events assessed by the investigator as exclusively related to underlying disease or medical

condition/concomitant treatment. If treatment must be delayed for reasons other than toxicity, contact the Medical Monitor to discuss the reasons for delay and plans for resuming study therapy.

- Treatment may be delayed up to 14 days. If the subject has completed two cycles and, in the investigator's opinion, is receiving benefit, treatment may be delayed for longer than 14 days and then resumed following a discussion with the Medical Monitor.
- Subjects who experience a toxicity requiring reduction in dose level may continue treatment at the lower dose level until disease progression or unacceptable toxicity. Once the dose has been reduced it may not be escalated to the starting dose.
- See **Appendix B** for FF-10501-01 dose modification requirements.

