5.5. Supportive Care Guidelines

- Medications may be administered for the management of symptoms associated with the administration of FF-10501-01, as required.
- Prophylactic pre-medication will not be used routinely. Adequate treatment for nausea and/or vomiting and diarrhea is permitted during Cycle 1. After Cycle 1, prophylaxis of nausea and/or vomiting and diarrhea is permitted.
- Granulocyte stimulating growth factors (e.g., G-CSF or GM-CSF) are not allowed during Cycle 1 except for the following situations (defined as DLTs): Grade 4 neutropenia lasting 7 days or more, or failure of the absolute neutrophil count (ANC) to recover to Grade 1 within 12 weeks. After Cycle 1, use of granulocyte growth factors are allowed for prophylaxis or management of neutropenia.
- Erythropoiesis-stimulating agents, transfusions, etc. are permitted for management of hematologic toxicities.

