7.1.8. Adverse Event and Serious Adverse Event Follow-Up

All AEs and SAEs should be followed until resolution, return to baseline, or until the point it is deemed that further recovery is unlikely. All measures required for AE management and the ultimate outcome of the AE will be recorded in the source document and AE CRF module.

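### A pre-existing cytopenia that worsens on treatment, with the drug not ruled out, must recover to Grade 0-1 before re-dosing, even when the subject started worse than that

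*Protocol*

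**What the plan says.** Protocol Section 3.1 provides for dose adjustment for adverse events in Phase 2a. Section 5.4.2 and Appendix B are the rule that does this.

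- **Recovery target.** For Grade 2 (first to third occurrence) and Grade 3 (first and second occurrence), Appendix B says "Interrupt until resolved to Grade 0-1". For Grade 4 the default is permanent discontinuation. If the physician continues in the subject's interest, the instruction is "interrupt and/or dose reduce until resolved to Grade 0-1". The fourth Grade 2 and third Grade 3 occurrences set no recovery target; they say discontinue or reduce.
- **Exemption.** Section 5.4.2: "Adverse events considered for treatment interruption and dose reduction will exclude the events assessed by the investigator as exclusively related to underlying disease", and likewise those due only to another medical condition or concomitant treatment.
- **Time limit.** Section 5.4.2: "Treatment may be delayed up to 14 days". A longer delay needs two completed cycles, benefit in the investigator's opinion, and a discussion with the Medical Monitor.
- **Entry.** Section 4.1 sets renal and hepatic limits but no minimum blood count. Its Grade 1 condition concerns acute toxicities of prior therapy. The response criteria in Section 7.2.2.2 provide for low pretreatment counts and transfusion dependence.
- **Baseline used elsewhere.** Section 7.1.8 sets how long the sites track an event: "All AEs and SAEs should be followed until resolution, return to baseline, or until the point it is deemed that further recovery is unlikely".

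**The concern.** Many subjects with MDS or CMML can be expected to start with low counts. A fixed Grade 0-1 target suits a toxicity that starts from normal. For a subject who starts below that level, it asks for a count better than the one at the first dose, and return to the pre-dose count does not satisfy it.

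At up to seven sites, an investigator whose subject is back at the pre-dose count but still above Grade 1 can stop treatment, judge the event exclusively disease-related, or deviate. Which of these happens would vary between investigators. Stopping early can cost a response, because objective response is counted within 3 cycles. Relabelling keeps an event with possible drug contribution out of interruptions and dose intensity, which inform the primary objective of tolerability.

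**Working it through.** The plan gives no figure on this point to reproduce. The check is mainly one of text.

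**Step 1. Which events reach the rule?** The rule acts on adverse events. Section 7.1.1 excludes pre-existing conditions that do not worsen, laboratory abnormalities that are not clinically significant, and disease worsening captured as efficacy. Section 7.1.5 does not record known study-condition laboratory changes that have not worsened. A stable baseline cytopenia therefore never reaches Appendix B. The exclusions that depend on no worsening lapse once the count falls.

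**Step 2. Does the exemption then apply?** Under Section 7.1.5.2 an event is possibly related when the drug cannot be excluded, even though disease is a presumable cause. Such an event is not exclusively disease-related, so it stays in the rule.

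**Step 3. What must the count do?**

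| Baseline grade | On-treatment grade | Target | Target relative to baseline |
|---|---|---|---|
| 0-1 | 2 or 3 | 0-1 | within reach of baseline |
| 2 | 3 | 0-1 | better than baseline |
| 2 or 3 | 4, treatment continued | 0-1 | better than baseline |

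The Grade 2 rows cause this difficulty only if a fall within Grade 2 is recorded as an adverse event.

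**Step 4. Is that recovery to be expected?** In the earlier Phase 2 study of the same active ingredient (Section 1.3.3), "recovery from nadir to pre-dose values was approximately 2 weeks". That fits the 14-day limit in time, but the level reached was the pre-dose value. One full 14-day delay is 14/84 = 17% of a three-cycle response window.

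**Step 5. How many subjects?** Let f be the share of the 20 Phase 2a subjects whose pre-treatment count is worse than Grade 1. The documents do not give it; 0.5 to 0.9 is assumed. Let w be the rate of drug-related marrow events, with f and w taken as independent.

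Expected number = 20 × f × w. Chance of at least one = 1 − (1 − f·w)^20.

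| Source of w | w | Expected of 20 | Chance of at least one |
|---|---|---|---|
| This study, Grade 3-4 (Section 1.7.2) | 1/33 = 3.0% | 0.30 to 0.55 | 26% to 43% |
| Earlier Phase 2 study, any grade (Section 1.3.3) | 14/165 = 8.5% | 0.85 to 1.53 | 58% to 80% |
| Japan study, Grade 4 neutropenia (Section 1.7.1) | 1/9 = 11.1% | 1.11 to 2.00 | 68% to 88% |

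**Step 6. What reaches the response rate?** Only a subject who would have responded can be a lost response. With an assumed response rate of 20% (4/20), expected lost responses are 0.2 × 0.30 = 0.06 to 0.2 × 2.00 = 0.40, or 0.3 to 2.0 percentage points. The chance of at least one is 1 − (1 − 0.2·f·w)^20, from 6% to 33%. This assumes that every affected subject stops before responding. The 90% Clopper-Pearson interval for 4/20 is 7.1% to 40.1%, about 33 points wide.

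**The case against.** The strongest reply is that this is a one-phrase gap in a conservative stopping rule, which is defensible for an early-phase antimetabolite. Several parts of it stand, and they rule out stronger readings that a reader might infer.

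- **That the exclusivity exemption is the only protection for disease-related cytopenia.** It is not. Sections 7.1.1 and 7.1.5 remove stable cytopenia, and disease worsening captured as efficacy, before the dose rule applies.
- **That the rule ends treatment in Cycle 1 or 2.** Section 5.4.2 limits delay but states no discontinuation consequence. Section 5.5 allows granulocyte growth factors after Cycle 1, and in Cycle 1 for prolonged Grade 4 neutropenia; transfusions and erythropoiesis-stimulating agents are permitted for hematologic toxicity. A Grade 4 event may be continued at a reduced dose.
- **That Grade 3 is handled more strictly than Grade 4.** The Grade 4 default is permanent discontinuation, and continuing starts at 50% of the dose, not 75%.
- **That relabelling hides the cytopenia.** SAP Section 3.4.2 summarizes treatment-emergent events whatever their cause. Section 3.4.3 grades all laboratory values, and Section 4.1.6.3 lists a shift table to the most extreme grade. Only interruptions and dose intensity are affected.
- **That affected subjects leave the per-protocol set.** The assessment at the end of Cycle 1 is not cancelled by an interruption.

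The counts in Step 5 are also soft. They do not require the same cell line to be low at baseline and then to fall. The 14/165 includes events of any grade, and Grade 1 needs no action. The Japan event was Grade 4, which can continue without interruption. Section 1.7.2 reports that this study's drug-related Grade 3 or 4 events resolved without sequelae. In the other direction, an event not exclusively due to disease is a wider class than a drug-related event.

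None of this supplies a baseline alternative for a worsening cytopenia with possible drug contribution.

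**Conclusion.** The point holds in a limited form. For a pre-existing cytopenia that worsens and is not judged exclusively disease-related, Section 5.4.2 with Appendix B sets a Grade 0-1 target with no return to baseline. A subject who starts worse than Grade 1 must then exceed the pre-dose count, normally within 14 days.

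That conclusion rests on the text alone. Its size does not. The documents cannot give the number affected, and the working range of about 0 to 2 of 20 depends on an assumed 50% to 90% share with low baseline counts and on rates from other doses and schedules. The effect on the response rate is smaller again, at most about 2 points under the assumptions shown, and well inside the interval's width. This is a cheap improvement to a rule that misfires in this population. It does not threaten the trial's conclusions.

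**What to change.** Amend Appendix B for hematologic toxicity only:

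- Set the recovery target to Grade 0-1 or the Cycle 1 Day 1 baseline grade, with baseline as in SAP Section 2.3.1.2.
- Apply the row only to a worsening of at least one CTCAE grade from baseline. For subjects already at Grade 4 at baseline, let worsening be agreed with the Medical Monitor.
- Keep the existing dose steps (75%, 50%, 25%) and the Section 5.4.2 exemption.
- Leave the non-hematologic rules unchanged, and apply the change from the amendment date forward.

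The cost is one row or footnote. The DLT definition and the endpoints do not change. The downside is that some subjects will resume at counts worse than Grade 1. After Cycle 1, hematology is scheduled only on Day 1 of each cycle (Section 6.3.1), so the sponsor may wish to add a mid-cycle count after resumption. The change does not depend on it.

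### Appendix B, read literally, allows reduced dosing without interruption through an unresolved Grade 4 event, a looser rule than for a first Grade 2 or 3 event, and it leaves the end of the reduction unclear beside Section 5.4.2

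*Protocol*

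**What the plan says.** Protocol Appendix B gives an action during a course of therapy and, beside it, doses under the heading "Dose Adjustment for Next Treatment".

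- **Grade 2, occurrences 1–3, and Grade 3, occurrences 1–2:** "Interrupt until resolved to Grade 0-1".
- **Grade 2, occurrence 4, and Grade 3, occurrence 3:** "Discontinue treatment permanently OR dose reduce", with reduction limited to the 200–400 mg/m² BID groups. No interruption and no resolution condition is stated.
- **Grade 4, first occurrence:** permanent discontinuation, or, "if physician deems it to be in the subject's best interest to continue", "interrupt and/or dose reduce until resolved to Grade 0-1", again for the 200–400 groups only. The next-treatment doses shown are 50% and 25% of the dose level.

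Section 5.4.2 refers the reader to Appendix B "for FF-10501-01 dose modification requirements", so the two texts apply together. It says that a subject who needs a reduction "may continue treatment at the lower dose level until disease progression or unacceptable toxicity", and adds: "Once the dose has been reduced it may not be escalated to the starting dose". No order of precedence between the section and the table is given.

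**The concern.** The table is the operative safety instruction for sites, and its 400 mg/m² BID column covers the Phase 2a regimen. The protocol's own fallback scale (Section 7.1.5.1) calls Grade 2 moderate and Grade 4 life-threatening or disabling. Yet the text makes a first Grade 2 event stop dosing and lets a Grade 4 event be handled by a lower dose alone. No reason is given.

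Two sites could therefore treat the same Grade 4 event differently, one with the subject off drug and one with the subject on drug, and both would comply. Safety and tolerability is the primary objective. Grade 4 hematologic toxicity lasting 7 days or more is a dose-limiting toxicity criterion in Section 3.1, so whether drug is taken during the event bears on a duration that the protocol itself uses.

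The second issue is what follows recovery. Tying a reduction to resolution suggests a temporary measure, while Section 5.4.2 gives a reduction a different end point.

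**Working it through.** **1. The table's own figures.** Reduced dose divided by dose level, Grade 4 row:

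- 100/200 = 150/300 = 200/400 = 50%
- 50/200 = 75/300 = 100/400 = 25%

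All six agree with the printed percentages. The issue is the wording, not the arithmetic.

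**2. The rows side by side.**

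| Row | Must dosing stop until Grade 0–1? | Reduce-only branch? |
|---|---|---|
| Grade 2, occurrences 1, 2, 3 | Yes | No |
| Grade 3, occurrences 1, 2 | Yes | No |
| Grade 2, occurrence 4 | Not stated, unless discontinued | Yes, 200–400 groups |
| Grade 3, occurrence 3 | Not stated, unless discontinued | Yes, 200–400 groups |
| Grade 4, occurrence 1 | Optional, unless discontinued | Yes, 200–400 groups |

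That is 3 + 2 = 5 rows with mandatory interruption and 3 rows without, of 8 in all. The broken layout of the Grade 3 and Grade 4 dose cells may come from the PDF conversion and is not counted against the plan.

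**3. What 'and/or' allows.** If the subject is not discontinued, there are three compliant actions: interrupt only, interrupt and reduce, or reduce only. Under the third, the subject takes drug while the Grade 4 event is unresolved.

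**4. Upper bound on dose taken during the event.** From the documents: 400 mg/m² BID for 21 days of a 28-day cycle (Section 1.8), and reduced levels of 200 and 100 mg/m² BID (Appendix B). Assumptions made here: the decision falls after Day 7, the event does not resolve by Day 21, and the next-treatment levels are also the levels used within the course, which the table does not say.

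Dose = reduced level × 2 per day × dosing days left. With 21 − 7 = 14 days left:

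- 50% level: 200 × 2 × 14 = 5,600 mg/m²
- 25% level: 100 × 2 × 14 = 2,800 mg/m²

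The total depends on the assumed day:

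- Decision after Day 14 (7 days left): 200 × 2 × 7 = 2,800 and 100 × 2 × 7 = 1,400 mg/m².
- Decision after Day 1 (20 days left): 200 × 2 × 20 = 8,000 and 100 × 2 × 20 = 4,000 mg/m².

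Earlier resolution lowers every figure. Under the interruption rows the corresponding amount before resolution is 0.

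**5. After resolution.** The Grade 4 row ties the reduction to resolution. Section 5.4.2 ties it to progression or unacceptable toxicity and bars the starting dose. The next-treatment column has no 100% entry for Grade 4. The texts can be applied together by keeping the subject on a reduced dose, but a site has to work that out for itself.

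**The case against.** The strongest reply is that Grade 4 is treated more strictly overall. Permanent discontinuation is listed first, at the first occurrence, whereas Grades 2 and 3 reach it only at occurrences 4 and 3. Continuing is a best-interest exception, and Sections 4.3.1 and 5.3 separately provide for stopping for unacceptable toxicity. On this view the looser wording is deliberate discretion. The default is indeed strict, and deliberate discretion is a possible reading. But the exception is exactly where the reduce-only option sits, so the default does not remove it. Nor does disease-driven cytopenia explain it, because Section 5.4.2 already sets aside events judged to be due solely to the disease, another condition or concomitant treatment.

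Other limits also stand:

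- A reader might infer that Grades 2 and 3 always require interruption and that Grade 4 is the lone exception. The last listed row of each lower grade shows otherwise.
- A reader might infer that Appendix B sends a subject back to full dose after a Grade 4 event, in direct conflict with Section 5.4.2. It does not say so. Its Grade 4 next-treatment entries are only 50% and 25%, Section 5.4.2 forbids the starting dose, and the words about resolution can be read with the interruption alone. Return to full dose is not a compliant option.
- The harm to the analysis should not be overstated. SAP Section 4.3 already plans listings of events leading to dose adjustment or interruption, of the medication diary and of dose-limiting toxicities, and no hypothesis test is planned. On-drug status during an event should be recoverable from these.

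**Conclusion.** The point holds in a limited form. Read literally, the Grade 4 exception permits reduced dosing without interruption during an unresolved event, which is looser than the rule for a first Grade 2 or Grade 3 event. Two further rows leave interruption unstated. The relation to Section 5.4.2 is an ambiguity about when a reduction ends.

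The 5,600 and 2,800 mg/m² totals are upper bounds for one assumed scenario, not expected exposures. The frequency at the Phase 2a dose cannot be derived. Section 1.7.2 reports drug-related Grade 3 or 4 events in 2 of 33 patients, at 200 and 300 mg/m² BID, without a clear split by grade. Section 1.7.1 reports one drug-related Grade 4 neutropenia among 9 patients in the Japanese study. Such events are therefore few but not hypothetical.

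A reader might also infer that interruption is the correct rule and the Grade 4 row the mistake. The documents do not establish that. They show only that the rows differ without explanation and need to be reconciled.

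**What to change.** The sponsor and Safety Review Committee should reconcile the Grade 4 row, Grade 2 occurrence 4, Grade 3 occurrence 3 and Section 5.4.2. Each row should give one unambiguous instruction on dosing before resolution and, separately, state what dose applies after resolution. The text should also make clear whether the next-treatment doses apply within the current course. The content is theirs to decide; no particular rule or dose is proposed.

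For Grade 4 events, including any already recorded, add two fields to the listing of treatment-emergent events leading to dose adjustment that SAP Section 4.3 already plans: whether drug was taken between onset and resolution, and at what dose. The medication diary supplies both.

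The cost is a few lines in a protocol amendment and two derived fields, with no new data collection. Depending on what is chosen, physicians may keep the present latitude or have less of it.
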